	24. Parent(s)/legal guardian(s) who are unable to communicate, read, or understand the local language(s). Subjects who are unable to communicate, read or understand the local language, or who display another condition, which in the Investigator's opinion, makes them unsuitable for clinical study participation.
	25. Subjects who are family members of the clinical study site, clinical study staff, or sponsor, or family members of enrolled subjects living in the same house.
Key Assessments:	Safety Assessments
	• Safety will be monitored through local tolerability assessments, vital signs, physical examination, safety labs, Children's Depression Inventory 2 (CDI-2, parent report for children 6-11 years old, inclusive), modified PHQ-A (for adolescents 12-17 years old, inclusive), PHQ-8 (for adults), C-SSRS (for adolescents and adults 12 years old and older), and AEs.

	• After obtaining consent, all AEs and TEAEs should be collected.					
	• The investigator or a properly trained and designated subinvestigator will perform local tolerability assessments at Baseline/Day 1, and Weeks 1, 2, and 4 (Days 8, 15, and 29). Subjects will have vital signs measured at each study visit. Height will be collected at Visit 1 (Screening) only.					
	 A limited physical exam (skin, lungs, and heart only) will be performed at Screening, Baseline/Day 1 and Week 4/Day 29. Blood and urine samples for routine safety laboratory tests (hematology, serum chemistry, and urinalysis) will be obtained at Screening, Baseline/Day 1 and Week 4/Day 29. For all female subjects of childbearing potential, a urine pregnancy test will be administered at all clinic visits except for Screening where a serum pregnancy test will be performed. A negative pregnancy result is required for continued participation in the study, and results (of the urine pregnancy test) must be available prior to dispensing of study drug at study visits. 					
	Efficacy Assessments					
	• Efficacy assessments will include vIGA-AD (Appendix 7), EASI, WI-NRS, BSA, DLQI/CDLQI (Appendix 8 and Appendix 9), DFI (Appendix 10), SCORAD (Appendix 11), and POEM (Appendix 12).					
	Pharmacokinetic Assessment					
	• A single PK assessment (trough) will be performed in all subjects with a blood sample collected at Week 4/Day 29.					
Study Endpoints:	 The Primary Efficacy Endpoint will be tested in all randomized subjects and defined as: 					

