- ^o On Day 8 and 15, dispensing of IP is optional. Site should review IP kit to ensure sufficient IP is available until the next visit and only dispense additional IP if needed. On Day 29, if the subject is unable to perform the Day 29 clinic visit due to COVID-19 restrictions (isolation, quarantine, etc.) then additional IP may need to be dispensed so IP can continue to be applied at home until the subject is able to return to the clinic to complete the Day 29 assessments (see IP Handling Manual for the process to dispense additional IP at or after Day 29).
- ^p Every tube should be weighed and recorded when dispensed and returned. See IP Handling Manual for details.
- ^q Compliance determination is described in the IP Handling Manual
- ^r All AEs should be collected starting after the first application of the investigational product through the end of the study. All SAEs should be collected starting after the signing of the informed consent through 30 days after the last day of the application of the investigational product or the end of the study (whichever is later). Any AEs (whether serious or non-serious) and clinically abnormal laboratory test values(s) will be evaluated by the PI and treated and/or followed up for up to 30 days after end of treatment or until symptoms or value(s) return to normal, or acceptable level, as judged by the PI
- ^s Subjects who enroll into the open label extension study (ARQ-151-313) must complete the ARQ-151-312 visit requirements at Week 4.

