5.7. Adverse Events

5.7.1. Adverse Event Definition

An AE is defined as any untoward medical occurrence associated with the use of a drug in humans, whether or not considered drug related. An AE can therefore be any unfavorable and unintended sign (including an abnormal laboratory finding), symptom, or disease temporally associated with the use of a medicinal (investigational) product, whether or not related to the medicinal (investigational) product.

A treatment emergent adverse event (TEAE) is defined as an AE that started post application of study medication at the Baseline visit or was present at treatment initiation but worsened during treatment, through study completion.

The definition of AEs includes worsening of a pre-existing medical condition. Worsening indicates that the pre-existing medical condition has increased in severity, frequency, and/or duration or has an association with a worse outcome. When recording such events, provide descriptions that the pre-existing condition has changed (eg, worsening hypertension for a subject with pre-existing hypertension). A pre-existing condition that has not worsened during the study or involves an intervention, such as elective cosmetic surgery or a medical procedure while on study, is not considered an AE.

Progression of atopic dermatitis including new or worsening of anticipated clinical signs or symptoms, which are collected as clinical efficacy variables and assessed as unequivocally associated with the disease progression and /or lack of efficacy, should NOT be reported as adverse events unless the disease progression is greater than anticipated in the natural course of the disease.

In general, abnormal laboratory findings without clinical significance (based on the investigator's judgment) are not to be recorded as AEs. However, abnormal laboratory findings that result in new or worsening clinical sequelae, or that require therapy or adjustment in current therapy, are considered AEs. Where applicable, clinical sequelae (not the laboratory abnormality) are to be recorded as the AE.

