6.8. Adverse Events

All TEAEs occurring during the study will be recorded and classified on the basis of MedDRA terminology for the safety population. TEAEs are defined as those AEs with an onset on or after the time of first study drug application. All reported TEAEs will be summarized by treatment group.

Descriptive statistics will be calculated for quantitative safety data and frequency counts will be compiled for classification of qualitative safety data.

Adverse Events:

The subject incidence of treatment-emergent adverse events (TEAE) will be summarized overall, by severity, and by attribution.

Clinical Laboratory Results:

Shifts in clinical laboratory parameters from baseline to worst post-baseline grade will be provided.

Vital Signs:

The subject incidence of >5% weight loss or gain on study will be provided, as well as whether weight loss was explained or unexplained.

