13.1 Adverse Events

Adverse events (AEs) will be coded according to the latest available version of Medical Dictionary for Regulatory Activities (MedDRA) (Version 23.0 or higher).

Treatment emergent adverse events (TEAEs) are defined as any AEs with onset on or after the first study drug application. See Appendix 2 for handling of completely or partially missing dates for AEs. In the case where it is not possible to define an AE as treatment emergent or not, the AE

	STATISTICAL ANALYSIS PLAN, Version 1.0
Protocol Number: ARQ-151-312	Sponsor: Arcutis Biotherapeutics, Inc.

will be classified as treatment emergent. All reported TEAEs will be summarized by treatment group.

Overall summary will be presented, which will include the total number of events, and the number and percentage of subjects who experienced TEAE, TEAE by the strongest relationship, TEAE by the maximum severity, treatment-related TEAE by maximum severity, treatment-emergent serious AE (TESAE), treatment-emergent Non-SAE, TEAE leading to study treatment discontinuation, TEAE leading to study discontinuation, TEAE on an application site, and TEAE leading to death.

The number and percentage of subjects who experience TEAE will be summarized by SOC and PT within SOC. In addition, similar table will be presented by treatment groups for age 6 to 17 years and ≥ 18 years separately. Unless otherwise specified, a subject experiencing the same TEAE multiple times will be counted only once for the corresponding PT. Similarly, if a subject experiences multiple TEAEs within the same SOC, the subject will be counted only once for that SOC. TEAEs will be sorted alphabetically by SOC and within each SOC the PT will be presented by descending frequency in the safety analysis set. A treatment-related TEAE is defined as any TEAE that is assessed by the Investigator as likely, probably, or possibly related to study treatment. TEAE that is assessed as unrelated or unlikely will be defined as not treatment-related. If a subject experiences more than one TEAE within different relationship categories within the same SOC/PT, only the worst case (the strongest relationship) will be reported. TEAE with an unknown relationship will be considered as treatment-related.

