- Missing day and month: Impute to January 1st, unless year is the same as year of first study treatment dose date then impute to the first study treatment date.
- Missing day: Impute to the 1st day of the month, unless month and year are the same as month and year of first study treatment dose date then impute to the first study treatment date.
- If imputed event start date is after event end date (imputed or not), set the event start date to the imputed event end date.

Event Start Time Imputation (for Adverse Events only)

Imputation of event end time should be done before imputation of event start date.

[figure not shown]
- If the event date is not the same as the first dose date or time part of the first dose date is missing, impute to 00:00.
- If the event date is the same as the first dose date and event occurred prior to study drug application (as flagged in CRF), impute to 00:00.
- If the event date is the same as the first dose date and event did not occur prior to study drug application (as flagged in CRF), impute to time part of first dose date.
- If the event start date is equal to event end date and imputed event start time is after event end time (imputed or not), set the event start time to the imputed event end time.

Event End Date Imputation

- Completely missing (and not flagged as "ongoing"): Impute to the last contact date.
- Missing day and month: Impute to December 31st, unless year is the same as last contact date then impute to the last contact date.
- Missing day: Impute to the last day of the month, unless year and month are the same as year and month of last contact date then impute to the last contact date.

Event End Time Imputation (for Adverse Events only)

Impute to 23:59.

Electronic Record and Signature Disclosure: Accepted: 08-Jun-2022 | 12:08 ID: 3f347f78-8c69-41a3-ab01-f48a0581f66e

In Person Signer Events	Signature	Timestamp
Editor Delivery Events	Status	Timestamp
Agent Delivery Events	Status	Timestamp
Intermediary Delivery Events	Status	Timestamp
Certified Delivery Events	Status	Timestamp
Carbon Copy Events	Status	Timestamp
Witness Events	Signature	Timestamp
Notary Events	Signature	Timestamp
Envelope Summary Events	Status	Timestamps
Envelope Sent Certified Delivered Signing Complete Completed	Hashed/Encrypted Security Checked Security Checked Security Checked	07-Jul-2022 07:05 07-Jul-2022 21:49 07-Jul-2022 21:50 07-Jul-2022 21:50
Daymant Frants		
Payment Events	Status	Timestamps

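### SAP 13.1 and Protocol 6.8 define a treatment-emergent event by onset alone, without the worsening limb of Protocol 5.7.1, so a pre-dose event that worsens on treatment and is not re-entered misses every TEAE table

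*SAP*

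**What the plan says.** Three places define a TEAE.

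- SAP 13.1: "Treatment emergent adverse events (TEAEs) are defined as any AEs with onset on or after the first study drug application". If an event cannot be classified, the same section treats it as treatment-emergent.
- Protocol 6.8, the protocol's analysis section: "TEAEs are defined as those AEs with an onset on or after the time of first study drug application".
- Protocol 5.7.1 has two limbs. The event started after application at Baseline, or it "was present at treatment initiation but worsened during treatment, through study completion".

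Protocol 5.7.1 also says "The definition of AEs includes worsening of a pre-existing medical condition", and on recording: "When recording such events, provide descriptions that the pre-existing condition has changed". It does not say whether to open a new record or which onset date to enter.

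The documents disagree on when AE collection starts. The Protocol 1.1 synopsis says "After obtaining consent, all AEs and TEAEs should be collected", the screening procedures in 5.1.1 include collecting adverse events, and the visit schedule marks AE assessment at Screening and Baseline. Footnote r to that schedule says "All AEs should be collected starting after the first application of the investigational product through the end of the study". Protocol 5.1.12 and 5.7.5 and the matching footnote in the SAP schedule agree with footnote r. SAEs are collected from consent throughout.

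SAP section 1 lets the SAP govern the analysis and sends changes from the protocol to section 3.5, which has no entry on TEAEs. SAP 13.1 lists all AEs, treatment-emergent or not.

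**The concern.** One safety endpoint has two definitions, and the analysis uses the narrower. An event already present at first application that becomes worse on treatment is treatment-emergent under 5.7.1. Under 6.8 and SAP 13.1 it is not, if its recorded onset stays pre-dose.

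The overall TEAE summary, relatedness, maximum severity, treatment-emergent SAEs and TEAEs leading to discontinuation all rest on this definition. An event that is non-serious before dosing and becomes serious on treatment, kept as one record, would also miss the treatment-emergent SAE table. For such a subject, the tables understate on-treatment harm. The listing still shows the event but gives no incidence by arm.

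**Working it through.** The plan states no figure to reproduce, so the check traces kinds of event through the definitions.

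1. **A medical-history condition worsens after first application and is entered as an AE dated at the worsening.** Onset is post-dose. It is a TEAE under 5.7.1, 6.8 and SAP 13.1. Nothing is lost.
2. **An AE or SAE is recorded with a pre-dose onset, worsens after first application, and stays one record with its original date.** It is a TEAE under the second limb of 5.7.1, but not under 6.8 or SAP 13.1. It is absent from every TEAE summary and present only in the listing.
3. **Timing relative to first application cannot be determined.** SAP 13.1 counts it as treatment-emergent, and Appendix 2 moves a completely missing start date to the first treatment date. Nothing is lost. This default does not help case 2, where a pre-dose onset is known.

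Only case 2 is lost. Whether such records can exist depends on what is collected:

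- SAEs: yes, from consent under every passage.
- Non-serious AEs: not under footnote r, 5.1.12, 5.7.5 or the SAP schedule footnote. They can exist where a site follows the synopsis line or the Screening and Baseline AE assessments.
- SAP Appendix 2 has a rule for when the "event occurred prior to study drug application (as flagged in CRF), impute to 00:00". It applies only when the event date equals the first-dose date, and only to fill in a clock time. It shows that same-day pre-dose records were foreseen, not that a body of screening-period AEs exists.

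Scale per subject, using the planned 650 randomized 2:1:

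- Active: 650 × 2/3 ≈ 433, so one lost subject lowers TEAE incidence by 1/433 ≈ 0.23 percentage points.
- Vehicle: 650 × 1/3 ≈ 217, so one lost subject lowers it by 1/217 ≈ 0.46 percentage points.

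These apply only to a subject with no other TEAE. The documents give no rate for case 2, so no total can be calculated.

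**The case against.** The strongest reply is that the gap hardly arises in practice. Four detailed passages start non-serious AE recording after first application, so a symptom beginning in screening would normally not be an AE record with a pre-dose onset. Worsening of a pre-existing condition is already an AE in its own right, and if dated at the worsening it meets SAP 13.1. Safety has no inferential tests. Laboratory values, weight, depression scores and suicidality are tabulated by visit or shift whatever the TEAE status. All of this stands, and it limits the reach. It does not cover pre-dose SAEs, or pre-dose AEs recorded under the synopsis, when one record is kept.

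A second reply is that the SAP changed nothing, because 13.1 matches the protocol's own analysis section. This also stands. A reader might infer that the SAP departed from the protocol without declaring it in 3.5. The documents do not support that: the conflict is between 5.7.1 and 6.8, and the SAP follows 6.8. The supplied protocol is marked Original while the SAP is based on Amendment 3, so whether the two sections still differ there cannot be checked.

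A third reply is that a programmed flag alone would not work. Protocol 5.7.5 records onset, duration, outcome and a maximum severity, and no dated grade history is described. From a single pre-dose record, neither the worsening nor its date may be derivable. This is correct, and the fix must include a recording instruction.

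**Conclusion.** The inconsistency is real and should be corrected, but its reach is narrow. It affects AEs or SAEs recorded with a pre-dose onset that worsen after first application and are not re-entered. These are probably few: mainly SAEs, plus any non-serious pre-dose AEs recorded because of the conflicting collection rules. The loss is nil if every worsening becomes a new AE dated at the worsening.

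A reader might infer that worsening on roflumilast in general drops out of the TEAE tables, or that insomnia, nausea or low mood beginning in the screening month would be lost as a matter of course. The documents do not support either. Most such symptoms would not be pre-dose AE records, and their worsening is an AE in its own right. Nor do the documents show a bias towards active treatment, because the rule is the same in both arms. Any percentage for the total loss would be an assumption without a source.

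**What to change.** Before unblinding:

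1. Add the worsening limb of Protocol 5.7.1 to SAP 13.1, so that a TEAE is an AE with onset on or after first application, or one present at first application that worsened during treatment. Align Protocol 6.8 with it.
2. Have any worsening after first application of a pre-dose AE entered as a new AE record dated at the worsening. Query existing pre-dose records for this, so that the flag can be derived.
3. Reconcile the synopsis, and the Screening and Baseline AE assessments, with footnote r, 5.1.12 and 5.7.5 on when AE collection starts.

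The cost is a small wording change in each document, one flag in the AE dataset, minor data-entry or query work, and a slightly higher TEAE count.

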13.2 Clinical Laboratory

Descriptive statistics for the observed values in chemistry, hematology, and quantitative urinalysis, change from baseline and percent change from baseline values will be presented by treatment group at each scheduled visit. For qualitative urinalysis data, the number and percentage of the subjects for each level of result by treatment at each scheduled visit will be provided.

Shift tables from baseline to each postbaseline assessments describing shifts to out-of-normal range will be provided for chemistry, hematology, and qualitative urinalysis. Only subjects with a baseline result and a result at the specified visit for the parameter will be considered.

Listings of abnormal laboratory will be provided for each parameter where a subject had at least one abnormal result.

Laboratory data will be presented in SI units.

13.3 Vital Signs

Descriptive statistics will be presented for vital signs (systolic blood pressure, diastolic blood pressure, heart rate, body temperature, and weight). Observed values, change from baseline and percent change from baseline values will be presented by treatment group at each scheduled visit.

The number and percentage of subjects with gain or lose >5% from baseline in body weight over the course of the study will be summarized for overall and separately for children and adolescents (6 to 17 years) and adults (\geq 18 years). BMI will be summarized using descriptive statistics (n, mean, standard deviation, median, Q1, Q3, minimum, and maximum) on observed values, change from baseline and percent change from baseline values separately for children and adolescents (6 to 17 years) and adults (\geq 18 years). The BMI percentile rather than BMI kg/m² will be summarized for children and adolescents (6 to 17 years).

A listing of all vital sign assessments including weight, BMI, and BMI percentile for children and adolescents will be provided.

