2.3.2. Oral Roflumilast Tablet

Oral roflumilast (DALIRESP[®]) has been approved globally for the treatment of COPD and has been evaluated in nine Phase III/IV randomized double-blind clinical trials (Wedzicha 2016). Overall, the safety of oral roflumilast has been well established in its targeted population of mostly middle- and upper-aged individuals who currently smoke cigarettes or have smoked them

Confidential

extensively in the past. Adverse events (AEs) reported with roflumilast tablets have been consistent with those expected for oral PDE-4 inhibitors. In a pooled analysis of safety data from 6-month and 1-year clinical trials (N=8630), the most common AEs were diarrhea, weight loss and nausea. Other AEs reported more frequently with roflumilast treatment than with placebo were back pain, influenza, insomnia and decreased appetite (Michalski 2012), (Wedzicha 2016).

In addition to the self-reported cases of weight loss in the 6-month and 1-year oral trials, clinically significant weight loss was also reported in two prospective studies that evaluated weight (Michalski 2012).

Psychiatric-related AEs were also greater in patients treated with roflumilast tablets (5.9%) compared to those treated with placebo (3.3%). The most common psychiatric-related AEs were insomnia, depression and anxiety. A small number of cases of completed suicide and suicide ideation have been reported in patients taking oral roflumilast in clinicals trials and also during post-marketing experience (Michalski 2012).

The only contraindication to oral roflumilast is use in patients with moderate to severe liver impairment (Child-Pugh B or C), where systemic levels of roflumilast may become elevated.

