8 DEMOGRAPHIC AND OTHER BASELINE CHARACTERISTICS

Demographics and baseline characteristics will be summarized with descriptive statistics using the ITT and safety population. The list of demographics and baseline characteristics to be summarized will include:

- Age (years)
- Age Group: 6-11, 12-17, 6-17 and \ge 18, 18-64 and \ge 65
- Child bearing potential
- Sex at birth
- Ethnicity
- Race*
- Baseline Height (cm)
- Baseline Weight (kg)
- Baseline Body Mass Index (BMI) (kg/m²): Adult, Child/Adolescent
- Fitzpatrick Skin Type

	STATISTICAL ANALYSIS PLAN, Version 1.0
Protocol Number: ARQ-151-312	Sponsor: Arcutis Biotherapeutics, Inc.

- Prior failure of Topical Corticosteroids, Topical Calcineurin Inhibitors, Eucrisa
- Atopic Dermatitis involvement on the face, on the eyelids
- Baseline vIGA-AD
- Average weekly baseline WI-NRS
- Daily baseline WI-NRS
- Baseline BSA (%)
- Baseline BSA (%) Group <10% and $\ge 10\%$, tertile groups
- Baseline EASI total score
- Baseline EASI score group \leq 7 and \geq 7, tertile groups
- Baseline SCORAD
- Baseline DLQI/CDLQI
- Baseline DFI
- Baseline POEM
- Baseline PHQ-8
- Baseline PHQ-A
- Baseline CDI-2

Adult: BMI $(kg/m^2) = (weight in kg)/[(height in cm/100)^2]$. Baseline height will be used to derive BMI for each visit since height is not collected at all visits.

Child and Adolescent (6 to 17 years): After BMI is calculated using the same formula above for children and teens, it is expressed as a percentile obtained from either a graph or a percentile calculator. Percentiles will be calculated using data files and instructions provided by the CDC (https://www.cdc.gov/growthcharts/percentile data files.htm). Baseline height will be used to derive BMI for each visit since height is not collected at all visits.

A listing of all demographics, analysis population flag, reason not included in the efficacy analysis will be provided.

^{*}Subjects who reported more than one race will be summarized as 'Multiple' races in the table. All races selected will be displayed in the listing.

	STATISTICAL ANALYSIS PLAN, Version 1.0
Protocol Number: ARQ-151-312	Sponsor: Arcutis Biotherapeutics, Inc.

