13 SAFETY ANALYSIS

Safety analyses will be conducted using the safety population. Subjects will be analyzed based on the treatment received and the stratum they belong to.

No formal inferential statistics will be performed on safety assessments.

Also, treatment-emergent adverse events by SOC and PT table and summary of weight change will be presented by treatment groups for age 6 to 17 years and \geq 18 years separately.

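### For ages 6 to 17, BMI is summarised as change and percent change of a percentile, a scale on which equal losses read very differently (minor; one descriptive table)

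*SAP*

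**What the plan says.** SAP Section 13.3 specifies descriptive statistics for BMI "on observed values, change from baseline and percent change from baseline values separately for children and adolescents (6 to 17 years") and for adults. It then sets the paediatric scale: "The BMI percentile rather than BMI kg/m² will be summarized for children and adolescents (6 to 17 years"). Read together, the two sentences put observed value, change and percent change on the percentile.

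SAP Section 8 explains the derivation. BMI is computed from weight and height, and for ages 6 to 17 "it is expressed as a percentile obtained from either a graph or a percentile calculator", using CDC data files. Baseline height is used at every visit.

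Weight is handled separately, on its own scale:

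- Section 13.3: "Descriptive statistics will be presented for vital signs (systolic blood pressure, diastolic blood pressure, heart rate, body temperature, and weight"). For these, "Observed values, change from baseline and percent change from baseline values will be presented by treatment group at each scheduled visit".
- Section 13.3: "The number and percentage of subjects with gain or lose >5% from baseline in body weight over the course of the study" is given overall and separately for ages 6 to 17 and for adults. Section 2 lists this incidence as a safety endpoint.
- Section 13: a "summary of weight change will be presented by treatment groups for age 6 to 17 years and" for adults, separately.
- Section 13.3: weight, BMI and BMI percentile are all listed.

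**The concern.** Weight is a safety variable of interest for this drug. Protocol Section 2.3.2 names weight loss among the most common adverse events of the oral form and adds that "clinically significant weight loss was also reported in two prospective studies that evaluated weight". Children and adolescents are a large share of the trial: adults are capped at 50% in the SAP schema (Section 3.1) and at 25% in Protocol Section 4.2, so at least half of the subjects should be 6 to 17.

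A percentile is a nonlinear transform bounded by 0 and 100. A child near the top can lose BMI with almost no movement in percentile. A child near the bottom has a very small denominator, so a small drop becomes a large percent change. A mean point change therefore mainly reflects mid-range children, and a mean percent change can be dominated by a few thin ones. Neither mean describes a common effect, and two arms with the same loss could show different means simply because their baseline BMI differs.

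**Working it through.** The documents give no figure for this point, so there is nothing to reproduce. Two illustrations follow. Both rest on assumed inputs, because the documents contain neither an expected effect on BMI nor the growth-chart parameters.

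**1. The same fall in z-score (assumed 0.2 SD)**

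Percentile = 100 × Φ(z), with Φ the standard normal distribution function. Point change = 100 × [Φ(z - 0.2) - Φ(z)]. Percent change = point change divided by the starting percentile.

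| Start z | Percentile before | Percentile after | Point change | Percent change |
|---|---|---|---|---|
| -2 | 2.28 | 1.39 | -0.9 | -39% |
| 0 | 50.0 | 42.07 | -7.9 | -16% |
| 2 | 97.72 | 96.41 | -1.3 | -1.3% |
| 2.5 | 99.38 | 98.93 | -0.45 | -0.5% |

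The point change is largest in the middle and shrinks in both tails: 7.93 / 0.451 is about 18-fold between the 50th and 99.4th percentiles. The percent change runs steadily from large at low BMI to almost nothing at high BMI: 38.9 / 0.454 is about 86-fold between the 2.3rd and 99.4th.

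**2. The same 5% weight loss**

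Height is fixed at baseline (SAP Section 8), so a 5% weight loss is exactly a 5% BMI loss. Take z = [(BMI/M)^L - 1] / (L × S), or ln(BMI/M)/S when L = 0. The assumed values are L = 0, -1, -2 and S = 0.10, 0.13, 0.16. Age drift over four weeks is ignored. Ranges are over all nine combinations.

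| Starting percentile | Point change | Percent change |
|---|---|---|
| 3rd | -1.6 to -2.6 | -54% to -86% |
| 50th | -12.6 to -20.5 | -25% to -41% |
| 97th | -1.0 to -5.6 | -1% to -6% |
| 99th | -0.3 to -2.5 | about 0% to -3% |

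The pattern is the same under every combination tried.

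**3. What the z-score does instead**

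In illustration 1 the change in z is -0.2 at every starting point, by construction. For a fixed 5% loss, the formula gives a change in z of [(0.95^L - 1)/(L × S)] × (1 + L × S × z).

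- L = 0: the change is ln(0.95)/S at every starting BMI, which is -0.51 (S = 0.10) to -0.32 (S = 0.16).
- L = -2, S = 0.16, the most skewed case: the first factor is (1.108 - 1)/(-0.32) = -0.338. The change is -0.338 × (1 + 0.32 × 1.881) = -0.54 at the 3rd percentile, -0.34 at the 50th, and -0.338 × (1 - 0.32 × 2.326) = -0.09 at the 99th.

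In that worst case the z-score varies about 6-fold (0.54 / 0.09). For the same L and S the percentile point change varies about 53-fold (13.2 at the 50th against 0.25 at the 99th). The z-score is much better behaved but still understates a proportional loss at very high BMI. Percent change in weight is -5% throughout, which is why the z-score table should be read beside it.

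**The case against.** The strongest reply is that the percentile table is supplementary. Weight itself is summarised by arm and visit, gain or loss above 5% is tabulated for ages 6 to 17, and a weight-change summary by age group is promised. With height fixed, percent change in BMI equals percent change in weight, so the undistorted measure is already planned. Safety analyses carry no formal inference, and BMI percentile feeds no endpoint, alpha allocation, sample size or stopping rule. This stands, and it sets the severity.

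It also disposes of a tempting stronger reading: that a paediatric weight effect as such is reported on the percentile scale and could be lost from the safety report. The documents do not support that. Only BMI is on the percentile scale.

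A second tempting reading is that the percentile exaggerates loss at low BMI on both statistics. It does so for percent change only; point change is compressed at low BMI too.

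It is also fair to say that the illustrations use assumed effects and tail positions, and that the baseline BMI distribution is unknown. The fold ranges therefore show how the scale behaves and do not predict the distortion in this trial's means.

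One gap remains. The continuous weight table in Section 13.3 is specified by arm and visit, not by age. Section 13 does not say whether its age-specific weight-change summary holds continuous change or only the categories above 5%. On the narrow reading, the only continuous weight-related summary explicitly specified for ages 6 to 17 is the one on the percentile scale, and a shift below 5% would not show in the categorical table.

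**Conclusion.** The point holds as a minor defect in one descriptive safety table. Change and percent change of a BMI percentile do not measure a consistent quantity. Under the assumed 0.2 SD fall, one effect reads as anything from -0.45 to -7.9 points and from -0.5% to -39%, depending on where the child starts. The direction of the distortion does not depend on the assumptions; its size does. It does not follow that weight loss in children would go unseen, because the weight-scale summaries in SAP Sections 2, 13 and 13.3 remain. The defect changes no endpoint, test or decision rule.

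**What to change.** In SAP Section 13.3, for ages 6 to 17:

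1. Summarise BMI-for-age z-score as observed value and change from baseline, derived from the reference files that Section 8 already names for the percentiles.
2. Delete percent change of the percentile, and do not replace it with percent change of the z-score, which is equally uninterpretable because z passes through zero.
3. Keep BMI percentile in the listing.

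In SAP Section 13, state that the weight-change summary for ages 6 to 17 includes continuous change and percent change in weight by arm and visit, as well as the categories above 5%.

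The cost is one derived variable and a few lines of SAP text, with no change to data collection. There is a small downside: z-scores are less familiar to clinical readers and may be less reliable at extreme BMI. How the reference files behave there cannot be checked from the documents. The explicit weight table covers that weakness.
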